## 6.5 Missing Data

Due to the study design, data will be reported as collected and no imputation methods of missing values will be performed, except for partial dates. Below it is addressed how missing information will be handled for partial dates and incomplete disease assessments.

When no imaging/measurement is done at all at a particular time point, the patient is not evaluable (NE) at that time point. If only a subset of lesion measurements are made at an assessment, usually the case is also considered NE at that time point, unless a convincing argument can be made that the contribution of the individual missing lesion(s) would not

Pfizer Inc. / Protocol: TTI-621-03/C4961003  
IQVIA Biotech (Confidential) Project # YXA42460

change the assigned time point response, which is most likely to occur in the case of PD (e.g., if only 2 of 3 baseline target lesions are assessed and result in a > 20% increase in the sum, then the patient would be assessed as a PD regardless of the missing lesion).

Partial dates are allowed on the eCRF for prior disease therapy start and stop dates, adverse event (AE) onset and end dates, concomitant medication start and stop dates, and concomitant procedure, procedure dates. An entry for the year is required in the eCRF system for each of these dates. Only the month and day may be entered as unknown. Dates from these forms will be reported in listings as collected. Every effort will be made to query missing dates.

For records with missing AE onset date, the following procedure will be employed for use in determining whether the AE is treatment emergent:

- AE onset dates with missing day and non-missing month will be assumed to occur on the first day of the non-missing month, except for AEs occurring in the month and year of first dosing, in which case the date will be imputed using the date of first dosing.
- AE onset dates with missing day and month will be assumed to occur on the first day of the non-missing year (*i.e.*, January 1), except for AEs occurring in the year of first dosing, in which case the date will be imputed using the date of the first dosing.
- AEs that are not ongoing and have an end date with missing day and non-missing month, they will be assumed to occur on the last day of the month, except when the end of study date or date of death is prior to the last day of the month. The date will be imputed as end of study date, or death date, whichever happens the earliest.
- AEs that are not ongoing and have missing month in the end date, the imputed end date should be set to the last day of the year 31DECYYYY, except when the end of study date or date of death is prior to the last day of the year. The date will be imputed as end of study date, or death date, whichever happens the earliest.

For records with a missing medication start and/or stop date, the following procedure will be employed for use in determining whether the medication is prior or concomitant:

- Medication start dates with a missing day and non-missing month will be assumed to occur on the first day of the non-missing month, except for medications occurring in the month of first dosing, in which case the date will be the date of first dosing.

Pfizer Inc. / Protocol: TTI-621-03/C4961003  
IQVIA Biotech (Confidential) Project # YXA42460

- Medication start dates with missing day and month will be assumed to occur on the first day of the non-missing year (i.e., January 1), except for medications occurring in the year of first dosing, in which case the date will be the date of first dosing.
- Medications that are not ongoing and have a medication stop date with a missing day and non-missing month will be assumed to occur on the last day of the non-missing month.
- Medications that are not ongoing and have a medication stop date with missing day and month will be assumed to occur on the last day of the non-missing year (i.e., December 31).

For records with a missing procedure date, the following procedure will be employed for use in determining whether the procedure is prior or concomitant:

- Procedure dates with a missing day and non-missing month will be assumed to occur on the first day of the non-missing month, except for procedures occurring in the month of first dosing, in which case the date will be the date of first dosing.
- Procedure dates with missing day and month will be assumed to occur on the first day of the non-missing year (i.e., January 1), except for procedures occurring in the year of first dosing, in which case the date will be the date of first dosing.

For records with a missing disease progression date from prior therapy, the following procedure will be employed for use in analyzing time to event endpoints:

- If the disease progression date is completely missing OR only the year is available, set as missing.
- If both year and month of disease progression date from are available and only day is missing, the date of disease progression will be imputed by the last day of the month.

For records with a partial death date, the following procedure will be employed for use in deriving time to event variables.

- The death date will be imputed by the earliest possible date that is not contradicting with any other available data in the database.

## 6.6 Timing of Analyses

This is an open-label study, so analyses may be performed as the study progresses, such as efficacy and safety analysis for publication purposes. No formal interim analysis will be performed.

Pfizer Inc. / Protocol: TTI-621-03/C4961003  
IQVIA Biotech (Confidential) Project # YXA42460

Details of analysis will follow each section described in this SAP and may include the following components:

- Disposition
- Protocol deviations
- Baseline characteristics: demographics, medical history, cancer history, concomitant medications and concomitant procedures
- Key components from efficacy analysis
- Key components from safety analysis

## 6.7 Analysis Populations

### 6.7.1 Full Analysis Set (FAS)

The FAS will include patients who were enrolled, allocated to treatment, and received at least one non-zero dose of study treatment.

This analysis population will be used for baseline summaries and the analysis of efficacy endpoints.

Patients will be classified according to the study treatment actually received. For patients who received a wrong study dose, they would be recoded in protocol deviation and dosing compliance; if the wrong dose occurred only once, the analysis will use the patients' initial planned dose as summary cohorts. If more than one wrong dose occurred, the analysis will use patients' actual dose as summary cohorts. If patients' doses were reduced, safety analysis will use the initial planned dose as summary cohorts. Patients receiving different dosing schedules will be presented in the listings only.

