## 6. General Analytical Considerations

### 6.1 Study Summaries and Tabulations

The definition of “treatment group” will be tabulated as follows:

- Dose escalation cohorts (Phase 1)
  - Dose 1 (0.2 mg/kg)
  - Dose 2 (0.7 mg/kg)
  - Dose 3 (2.0 mg/kg)
- Expansion cohorts (Phase 2)
  - Cohort A (0.2 mg/kg)
  - Cohort B (1.0 mg/kg)
  - Cohort C (2.0 mg/kg)
- Pooled cohorts by dose level
  - Lower dose (0.2 mg/kg)

Pfizer Inc. / Protocol: TTI-621-03/C4961003  
IQVIA Biotech (Confidential) Project # YXA42460

- Higher dose (2.0 mg/kg)
- Overall
  - Phase 1 total
  - Phase 2 total
  - Phases 1 + 2 total (for non-efficacy summaries only)

Data will be summarized by treatment group as above, as applicable.

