## 8.2 Primary Efficacy Outcome Analysis

Baseline documentation of “target” and “non-target” lesions (lesion count and maximum lesion length) will be recorded in listings. The sum of diameters will be calculated for all target lesions at baseline and at each subsequent tumor assessment as a measure of tumor burden. The baseline lesion size value will be used as reference by which to characterize the lesion response.

Other lesions (or sites of disease) not selected as target lesions (measurable or non-measurable), including pathological lymph nodes, should be identified as non-target lesions and should also be recorded during screening. Measurements of these lesions are not recorded, but the presence or absence of each, including any progression, should be noted throughout the study. The appearance of new malignant lesions denotes disease progression.

Per RECIST criteria, target lesions considered ‘too small to measure’ will be assigned a default value of 5 mm and those identified as ‘not present’ will be assigned 0 mm for purposes of analysis.

All FAS patients will be included in the denominators for percentage, even if the patient had a NE response. The ORR and uORR will be summarized descriptively for RECIST assessment method, with a 95% confidence interval (CI) using Wilson’s score method.

Overall tumor response assessment data will be presented in listings.

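### SAP 6.7.1 classifies a patient by an undefined actual dose after two or more wrong doses, so cohort membership for efficacy depends on time on treatment

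*SAP*

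**What the plan says.** SAP 6.7.1 defines the Full Analysis Set (FAS) and the cohort in which each patient is counted. It gives two rules for dosing errors:

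- One error: "if the wrong dose occurred only once, the analysis will use the patients' initial planned dose as summary cohorts".
- Two or more: "If more than one wrong dose occurred, the analysis will use" the dose actually received to set the summary cohort.

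Protocol-driven dose reductions have their own sentence, limited to safety: "If patients' doses were reduced, safety analysis will use the initial planned dose as summary cohorts". For efficacy after a reduction, nothing is said beyond the general statement that patients are classified by the treatment they received.

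The scope of the FAS is stated in the same section: "This analysis population will be used for baseline summaries and the analysis of efficacy endpoints". SAP 8 uses it for every efficacy endpoint, and SAP 8.2 adds for response rates: "All FAS patients will be included in the denominators for percentage". SAP 6.7.2 makes the safety set identical to the FAS.

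The available columns are in SAP 6.1: 0.2, 0.7 and 2.0 mg/kg in escalation, 0.2, 1.0 and 2.0 mg/kg in expansion, plus pooled and overall groups. "Data will be summarized by treatment group as above, as applicable".

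**The concern.** The cohort in which a patient is analysed should be fixed at the start of treatment. Here it can change with a cumulative count that accrues during treatment. The count takes no account of how large the errors were, when they occurred, or how many infusions were correct. Two small errors in 27 infusions trigger the switch; one error in a single infusion does not.

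Exposure is itself an outcome. Dosing continues until progression or unacceptable toxicity (SAP 9.1), so a patient who progresses at the first scan has few chances to accumulate two isolated errors and a patient with lasting benefit has many. Loss from the assigned cohort would then be linked to the endpoints being estimated: response, PFS and OS.

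The rule also cannot be programmed as written. Actual dose could mean the mean, the most frequent or the last dose. An off-level value such as 1.6 mg/kg matches no column in SAP 6.1. The destination is unclear as well, because SAP 4.3.2 gives Cohort B as 2 mg/kg and Cohort C as 1 mg/kg, while SAP 6.1 gives B as 1.0 and C as 2.0.

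**Working it through.** **1. The plan's own figure.** SAP 4.3.2 gives a Simon design for 10% against 25%: 18 patients, continue with at least 2 responses, 13 more, success with at least 5 of 31, one-sided error 0.20, power 90%. The exact probability of success at response rate p is

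sum over x = 2 to 18 of C(18,x) p^x (1−p)^(18−x) × P[Bin(13,p) ≥ max(0, 5−x)].

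This gives 0.182 at p = 0.10 and 0.902 at p = 0.25. The stated design reproduces.

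**2. Number of TTI-621 infusions, k.**

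- First scan, after two cycles (Protocol 5.1): 2 × 2 = 4.
- Response confirmed on the first two scheduled scans, after Cycles 2 and 4 (SAP 8.1 requires two determinations at least 4 weeks apart): 2 × 4 = 8.
- End of the combination period: 2 × 6 = 12.
- The estimated 11 months of treatment (Protocol synopsis): 11 × 30.4375 / 7 = 47.8 weeks; (47.8 − 18) / 4 = 7.46 monotherapy cycles; 12 plus 14 or 15 = 26 to 27.

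**3. Chance of reaching two errors.** Assume independent errors at rate e per infusion. The documents give no value for e, so a range is shown.

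P(at least 2) = 1 − (1−e)^k − k e (1−e)^(k−1)

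Example, e = 2%, k = 4: 1 − 0.92237 − 0.07530 = 0.0023.

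| e (assumed) | k = 4 | k = 8 | k = 12 | k = 27 | ratio, 27 to 4 |
|---|---|---|---|---|---|
| 0.5% | 0.015% | 0.07% | 0.16% | 0.81% | 54 |
| 1% | 0.06% | 0.27% | 0.62% | 3.0% | 50 |
| 2% | 0.23% | 1.0% | 2.3% | 10.1% | 43 |
| 5% | 1.4% | 5.7% | 11.8% | 39.4% | 28 |

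Against a patient stopping at the first scan, the risk is 4 to 5 times higher at 8 infusions and 8 to 11 times higher at 12. The ratios are large, but at low e the absolute risks are small.

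**4. Who would move.** Illustrative 31-patient cohort (assumed: 5 responders with 20 infusions, 13 stable disease with 12, 13 early progressors with 4). Expected moves are the number of patients times P(at least 2):

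| e (assumed) | responders | stable disease | early progressors | P(at least one responder moves) |
|---|---|---|---|---|
| 0.5% | 0.02 | 0.02 | 0.002 | 2% |
| 1% | 0.08 | 0.08 | 0.008 | 8% |
| 2% | 0.30 | 0.30 | 0.03 | 27% |
| 5% | 1.32 | 1.54 | 0.18 | 78% |

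Responders are 5/31 = 16% of this cohort but 43% to 50% of expected moves. Most of the rest are stable disease.

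**5. Effect of one move.** Taking the Cohort A FAS as 31 patients, 5/31 = 16.1% (Wilson 95% CI 7.1 to 32.6) becomes 4/30 = 13.3% (5.3 to 29.7). Under classification by assigned cohort the chance of a move is zero at any exposure, and 5/31 stands.

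**The case against.** The strongest reply is that the problem may be negligible. Infusions are given by site staff (Protocol 8.5), the dose is recalculated each cycle (Protocol 5.2.3), and dosing errors are notified to the sponsor within 24 hours (Protocol 13.5.11). At 0.5% to 1% per infusion, only 0.8% to 3% of patients would reach two errors even after 27 infusions. This stands: the size is unknown and may be very small.

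Four stronger readings are tempting, and the documents do not support them:

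- **That responders in particular are removed.** The gradient follows time on treatment, so long stable disease shares it. It also assumes isolated errors. A systematic error from Cycle 1 would move an early progressor too, and that is the case an as-treated rule naturally addresses.
- **That two errors always move a patient.** If actual dose meant the most frequent dose, two errors in 27 infusions would move nobody. The contrast with the one-error sentence implies a switch, but the SAP does not say so outright.
- **That patients can be reassigned once results are known.** The rule is pre-specified and mechanical, and SAP 7.3 has deviations finalised before database lock and the efficacy analyses.
- **That the rule overturns the go decision in every expansion cohort.** Cohort B enrollment ended at 18 patients and the Simon design does not apply to Cohort C (SAP 4.3.2), so the 31-patient example concerns Cohort A only. Protocol 12.2 also gives the Simon decision its own response-evaluation population, to which SAP 6.7.1 does not say its rule applies. Efficacy analyses are descriptive (SAP 8), and a one-responder shift lies well inside the confidence interval.

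None of this supplies a reason to let an error count set cohort membership for efficacy.

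**Conclusion.** The point holds in limited form. A stated rule makes cohort membership for ORR, PFS and OS depend on a post-baseline count, and it uses a term that is not defined. For isolated errors unrelated to response, the direction follows from the design: a cumulative count cannot fall, so the chance of reaching two rises with time on treatment.

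The size rests on an assumed error rate and on reading actual dose as something other than the planned dose after two errors. Within 0.5% to 5%, it runs from practically nothing to a material chance that at least one responder leaves a cohort. In small cohorts one such move is visible in the reported rate. The change is worth making because it removes a possible bias and an ambiguity, not because serious distortion has been shown.

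**What to change.** Amend SAP 6.7.1 as follows:

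1. Analyse all efficacy endpoints by assigned (initial planned) dose cohort for every FAS patient, whatever the number of dosing errors. Say that this also covers patients with dose reductions, on which the efficacy text is silent.
2. List dosing errors as protocol deviations, with the tolerance that makes a dose wrong.
3. For safety, define actual dose by one fixed rule that does not depend on the cumulative error count. An example is the dose level given at most Cycle 1 infusions; as Cycle 1 has only two, let a tie default to the planned dose. Simply using the first infusion would reclassify a patient after a single Day 1 error. State how an off-level dose is tabulated.
4. Show actual-dose grouping for efficacy, if wanted, only as a sensitivity analysis under the same definition.
5. Reconcile the Cohort B and C dose labels between SAP 4.3.2 and SAP 6.1.

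The cost is SAP wording and slightly simpler programming. Data collection, sample size and trial conduct do not change.

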### 6.7.2 Safety Analysis Set (SAS)

The SAS is identical to the FAS, which will include patients who were enrolled, allocated to treatment, and received at least one non-zero dose of study treatment.

This analysis population will be used for the analysis of safety and exposure.

### 6.7.3 DLT-Evaluable Set (DES)

The DES is applicable to dose-escalation cohorts only. It will include patients who received the full dose of doxorubicin in Cycle 1 Day 1 and the planned doses of PF-07901800 on Day 1 and Day 8, and

Pfizer Inc. / Protocol: TTI-621-03/C4961003  
IQVIA Biotech (Confidential) Project # YXA42460

have been followed for the entire 21-day DLT period (Cycle 1) or who have a DLT during Cycle 1.

## 6.8 Data Display Characteristics

Data displays produced for this study will include three types—summary tables, data listings, and figures. Unless stated otherwise, data listings will be produced for all recorded data. Additional data listings will be produced for outcome measures that involve extensive procedures to derive the analyzed outcomes. Summary tables and figures will be produced when specified in sections to follow. All analyses will be performed using SAS (Statistical Analysis Software).

Data listings will simply list the data recorded on the CRF or derived for each subject. As needed, they can be ordered by dose cohort, site, subject number, and time of assessment, and additional levels of ordering hierarchy may reflect subsets of assessments within subject. Subject-level identifiers appear on the first line of data, and identifiers for subgroups within subject appear only on the first line of each subgroup value.

Tables will display summary statistics calculated for each dose cohorts per study phase (escalation/expansion), unless described otherwise in the following sections. For most summary tables, the dose group will be presented in column and the summary statistics of interest will be presented in rows. About tables labelling, the text “Number (%) of Subjects” will be incorporated in the title, either the primary title or as a separate subtitle, and no further labeling (e.g., “n (% )”) will appear in the body of the table.

The summary statistics displayed will be a function of the type of data associated with the summarized assessment. Unless stated otherwise in relevant sections to follow, continuous data will be summarized with the number of non-missing values, mean, standard deviation, minimum, median, and maximum. Categorical data will be summarized with the number of non-missing values and the numbers of values equal to each of the possible values. Percentages of subjects with each of the possible values will be calculated from the number of subjects in the corresponding analysis population, unless stated otherwise, and those percentages will be presented with one decimal (XX.X%). Some continuous variables may also be grouped into categorical levels and evaluated in frequency tables.

Pfizer Inc. / Protocol: TTI-621-03/C4961003  
IQVIA Biotech (Confidential) Project # YXA42460

Dates in the clinical database are classified into the categories of procedure dates, log dates, milestone dates, outcome dates, and special dates:

- Procedure Dates (TARGET DATE): Dates on which given protocol-specified procedure are performed. They include the dates of laboratory testing, physical examinations, disease assessments, etc. They should be present whenever data for a protocol-specified procedure is present and should only be missing when a procedure is marked as NOT DONE in the database. Procedure dates will not be imputed.
- Log Dates: Dates recorded in CRF data logs. Specifically, they are the start and end dates for adverse events and concomitant medications/procedures. They should not be missing unless an event or medication is marked as ongoing in the database. Otherwise, incomplete log dates will be imputed according to the rules in Section 6.3 above. However, in listings, log dates will be shown as recorded without imputation.
- Milestone Dates: Dates of protocol milestones such as study drug start date, study drug termination date, study closure date, etc. They should not be missing if the milestone occurs for a subject. They will not be imputed.
- Outcome Dates: Dates corresponding to study endpoints such as survival, progression, etc. In most cases, they are derived either from a milestone (e.g., the survival date is derived from the death date), or a procedure date (e.g., the progression date is derived from the date of the tumor scan that was used to determine progression). They may be subject to endpoint-specific censoring rules if the outcome did not occur but are not otherwise subject to imputation.
- Special Dates: Dates that cannot be classified in any of the above categories and they include the date of birth. They may be subject to variable-specific censoring and imputation rules.

Calculations using dates (e.g., subject's age or relative day after the first dose of study medication) will adhere to the following conventions:

- Trial Day 1 of Cycle 1 is defined as the day on which the dose of Doxorubicin and PF-07901800 is administered after screening. Study days after trial day 1 will be calculated as the difference between the date of interest and the first date of dosing of study medication plus 1 day. The generalized calculation algorithm for relative day:  $\text{STUDY DAY} = [(\text{TARGET DATE} - \text{DSTART}) + 1]$  where DSTART = the start day of study drug].
- For dates of interest before the first date of dosing of study medication, the study day will be calculated as:  $\text{STUDY DAY} = \text{TARGET DATE} - \text{DSTART}$ . Negative study days are reflective of

Pfizer Inc. / Protocol: TTI-621-03/C4961003  
IQVIA Biotech (Confidential) Project # YXA42460

observations obtained prior to first study drug administration.

Note: Partial date for the first study drug is not imputed in general.

All effort should be tried to avoid incomplete study drug start date.

- Age (years) at informed consent will be calculated as: (Date of informed consent – date of birth + 1) / 365.25, and then truncated to an integer. In case of partial birth date: impute missing day as 15th of the month; impute missing month as July (month 7); set missing age in case of missing year.
- Duration will be calculated by the difference of start and stop date + 1. AE duration (days) = AE end date – AE start date +1
- Study drug exposure duration (weeks) is detailed in section 9.1. Exposure.
- Time since disease diagnosis (months) will be calculated as (Informed Consent Date – Diagnosis Date + 1) / 30.4167.
- The time to event will be calculated as date of event minus reference date + 1. The specific censoring rules on time to event endpoints will follow Section 8 (for efficacy and PRO) and Section 9 (for ECOG performance status).
- The following conversion factors will be used to convert days to months or years:
  - 1 month = 30.4375 days
  - 1 week = 7 days
  - 1 year = 365.25 days

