- o Detailed sample collection schedule provided in [Table 25](#)
- p Detailed sample collection schedule provided in [Table 27](#)
- q Detailed sample collection schedule provided in [Table 26](#)
- r Detailed sample collection schedule provided in [Table 27](#)
- s Assessed every 12 ± 2 weeks; telephone contact is acceptable
- t Does not need to be performed if previous assessment was within 72 previous hours
- u Prior to initiation of Cycle 3, Cycle 4 and Cycle 6; does not need to be performed if previous assessment was within seven days
- v Prior to initiation of every third cycle (Cycle 7, Cycle 10, Cycle 13, etc.); does not need to be performed if previous assessment was within seven days
- w Prior to initiation of Cycles 5 and 8; does not need to be performed if previous assessment was previous four weeks
- x Participants with an unresolved AE considered by the Investigator as possibly related to or associated with [REDACTED] will be asked to return for [REDACTED] blood sampling at approximately 3-month intervals (if feasible given the underlying disease) until the last follow-up of the AE up to a maximum of 12 months. [REDACTED]
- y Cycles 2, 3, 4, 5 only
- z Cycle 2 and Cycle 3 only
- aa Every second cycle (Cycle 7, Cycle 9, Cycle 11, etc.)
- bb Cycle 7 only
- CCI**  
[REDACTED]
- dd May be collected anytime within seven days prior to and 14 days after Cycle 3 Day 1; other times may be acceptable after consultation with Sponsor
- CCI**  
[REDACTED]
- ff To be performed 30 + five days after last administration of study treatment or before initiation of subsequent anti-cancer therapy, whichever occurs first

Table 25. Sample Collection Schedule for Analysis of CCI

Cycle	CCI
Day of Cycle	
Timepoint(s)	

CCI

Table 26. Sample Collection Schedule for Analysis of CCI

Cycle	CCI
Day of Cycle	
Timepoint	

CCI

Table 27. Sample Collection Schedule for Analysis of [REDACTED]

Screening	CCI	CCI
CCI		

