## 9. Safety Analyses

Summary of AEs and other safety parameters will be based on the SAS by treatment group as described in Section 6.1, except for the DLT, which will be based on DLT-Evaluable Set (DES) by treatment group.

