## 9.8 Electrocardiograms

Supine position 12-lead ECGs will be performed at screening and reviewed locally at each visit.

Corrected QT, PR and QRS data will be collected on the ECG eCRF page. Data will be summarized using QTc.

The frequency (number and percentage) of participants with notable ECG values according to the following categories will be summarized:

- QTc increase from baseline >30 ms, >60 ms
- QTc > 450 ms, > 480 ms, > 500 ms
- PR  $\geq$  220 ms and increase from baseline  $\geq$  20 ms
- QRS  $\geq$  120 ms

Participants with notable ECG interval values and qualitative ECG abnormalities will be listed for each participant and time point and the corresponding notable values and abnormality findings will be included in the listings.

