## 9.9 Transthoracic echocardiogram or Multigated Acquisition Scan

Patients must undergo a Transthoracic Echocardiogram (ECHO) or Multigated Acquisition (MUGA) Scan during the screening period, as well as in Cycle 5 day 1, Cycle 8 day 1 and in the Safety Follow-Up Visit, unless performed within previous 4 weeks. Left Ventricular Ejection Fraction (LEVF) and an overall interpretation (normal/abnormal) will be summarized by visit.

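### By-visit percentages of abnormal LVEF are divided by all treated patients, so at Cycle 5 and Cycle 8 they understate the proportion among those scanned

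*SAP*

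**What the plan says.** The general rule is in SAP 6.8: "Percentages of subjects with each of the possible values will be calculated from the number of subjects in the corresponding analysis population", with an exception only where another denominator is stated. The sentence before it adds a display requirement: "Categorical data will be summarized with the number of non-missing values and the numbers of values equal to each of the possible values". The non-missing count is therefore shown but does not serve as the denominator.

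SAP 9 fixes the population for safety tables: "Summary of AEs and other safety parameters will be based on the SAS by treatment group as described in Section 6.1". SAP 6.7.2 defines that set as enrolled and allocated patients who "received at least one non-zero dose of study treatment". No post-baseline measurement is required.

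For cardiac imaging, SAP 9.9 says that LVEF and "an overall interpretation (normal/abnormal) will be summarized by visit". It gives no denominator. The scans fall at screening, Cycle 5 Day 1, Cycle 8 Day 1 and the Safety Follow-Up Visit. Footnote w to Protocol Table 24 places the on-treatment scans "Prior to initiation of Cycles 5 and 8", and both documents waive a scheduled scan if one was done in the previous four weeks. SAP 6.5 imputes nothing except partial dates.

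**The concern.** A patient without a scan at a visit cannot enter the numerator for that visit but stays in the denominator. For the response rate, SAP 8.2 deliberately keeps non-evaluable patients in the denominator, and that is conservative. Applied to a toxicity measure, the same convention works in the favourable direction.

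The affected visits matter. The protocol caps doxorubicin at six cycles because of cumulative cardiac toxicity, and Cycle 8 Day 1 is the first scheduled on-treatment scan after that course ends. It is also the on-treatment visit with the most patients gone, so its percentage is diluted most. At screening nearly everyone should have a value, because LVEF is an eligibility criterion. A row of percentages running from screening to Cycle 8 therefore mixes cardiac findings with loss of ascertainment. The tables are also laid out by dose cohort, so cohorts with different rates of early departure would not be comparable on this row.

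**Working it through.** The documents give no LVEF percentage to reproduce. The first step is a reading of the text; the second illustrates size.

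**Which denominator applies.** SAP 6.8 gives the analysis population unless another is stated. SAP 9 and 6.7.2 make that population all treated patients. SAP 9.9 states nothing else. Elsewhere the SAP does name its denominators: dose-level counts for concomitant medication in 7.1, the full analysis set for disposition in 7.2, and all full-analysis-set patients for response in 8.2. So in 9.9 the default governs:

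- Printed percentage = abnormal at visit / all treated.
- Percentage among assessed = abnormal at visit / scanned at visit.
- Ratio of printed to assessed = scanned at visit / all treated.

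The ratio cannot exceed 1, so the direction is certain. Only the size needs an assumption.

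**Inputs for the illustration.**

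- Days from first dose: Cycle 5 Day 1 = 4 × 21 = 84; Cycle 8 Day 1 = 6 × 21 + 28 = 154.
- Days per month: 30.4375 (SAP 6.8).
- Time on study: assumed exponential. Medians of 3 and 5 months are the progression-free survival that both documents cite for doxorubicin, used as a proxy. A median of 11 months borrows the protocol synopsis's estimate of treatment length.
- Cohort size: 31, the planned expansion cohort (SAP 4.2). SAP 4.3.2 records that Cohort B closed at 18 and that 13 patients went to Cohort C; the ratio does not depend on size except through rounding.
- Everyone still on study is assumed to be scanned. Skipped scans would lower the ratio further.

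**Formula.** Fraction on study = 0.5^(t / median), with t in months: 84 / 30.4375 = 2.76 and 154 / 30.4375 = 5.06. Example: 0.5^(5.06 / 3) = 0.311.

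| Visit | Median (months) | Fraction = ratio | Still on study, of 31 | 3 abnormal / 31 | 3 abnormal / scanned |
|---|---|---|---|---|---|
| C5D1 | 3 | 0.529 | 16 | 9.7% | 18.8% |
| C5D1 | 5 | 0.682 | 21 | 9.7% | 14.3% |
| C5D1 | 11 | 0.840 | 26 | 9.7% | 11.5% |
| C8D1 | 3 | 0.311 | 10 | 9.7% | 30.0% |
| C8D1 | 5 | 0.496 | 15 | 9.7% | 20.0% |
| C8D1 | 11 | 0.727 | 23 | 9.7% | 13.0% |

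**Across visits.** Suppose 10% of scanned patients are abnormal at both visits. With medians of 3 to 5 months the table prints 5.3% to 6.8% at Cycle 5 and 3.1% to 5.0% at Cycle 8: a constant rate appears to fall.

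**Across cohorts.** With the same 10% among those scanned at Cycle 8, a cohort with a 3-month median prints 3.1% and one with a 5-month median prints 5.0%.

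**The case against.** Several points on the other side stand and limit the concern.

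- A reader might infer that unscanned patients are tabulated as normal. They are not. The normal and abnormal counts shrink together, the two percentages stop summing to 100%, and the non-missing count is displayed, so the loss is visible and the ratio recoverable. The printed percentage is still the diluted one.
- A reader might infer that LVEF itself will look better over time. SAP 9.9 also summarises LVEF, and SAP 6.8 summarises continuous data on non-missing values. Only the normal/abnormal interpretation is exposed.
- A reader might infer that early leavers escape cardiac assessment. They are due an LVEF at the Safety Follow-Up Visit, which Protocol 11 waives only for a scan in the previous four weeks with no abnormalities. Their results should appear in another row, and adverse events are tabulated separately. The distortion concerns the Cycle 5 and Cycle 8 rows, not the whole safety picture.
- The attrition figures are soft. Progression-free survival is not time on study: Protocol 5.3 allows treatment beyond progression.
- The percentage among those scanned is not an unbiased truth either, because that group is selected by remaining on study.

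A reader might also extend the point to the QTc categories in SAP 9.8, where "The frequency (number and percentage) of participants with notable ECG values according to the following categories will be summarized". The documents do not support a material effect. That count is not by visit, and a count of patients ever affected over all treated patients is a legitimate display. The first repeat ECG falls at Cycle 3 Day 1, the same visit as the first tumour scan, so radiographic progression will seldom remove patients before it, and a Safety Follow-Up ECG is scheduled. If 1 to 5 of 31 patients had no post-baseline ECG (an assumption), 3 cases would print as 3/31 = 9.7% against 3/30 = 10.0% to 3/26 = 11.5%.

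**Conclusion.** The point holds for the by-visit LVEF interpretation. Followed as written, the SAP divides the Cycle 5 and Cycle 8 abnormal counts by all treated patients. The printed percentage is too low, as a description of those assessed, whenever any treated patient lacks a scan at that visit. This presumes that percentages accompany the counts, as 6.8 provides; 9.9 itself does not mention them.

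The size is illustrative and rests on exponential time on study. At Cycle 8 the printed figure is about 31% to 50% of the assessed value for medians of 3 to 5 months, and about 73% for 11 months. At Cycle 5 the corresponding figures are 53% to 68%, and 84%.

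The documents do not support the wider claims that unscanned patients count as normal, that the continuous LVEF results are distorted, or that QTc is materially affected. The Simon decision rule uses response counts, so these percentages do not enter it. They do describe the safety of the selected doses, which is a primary objective.

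**What to change.** Add to SAP 9.9: percentages for the by-visit normal/abnormal LVEF interpretation use the Safety Analysis Set patients with a non-missing result at that visit, and that number is shown for each visit and treatment group. SAP 6.8 already permits such an exception, and the non-missing count is already part of its categorical display.

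The cost is one sentence and a changed denominator in the LVEF table program; no new data are needed. The drawbacks are that denominators will differ by visit, some percentages will be less favourable, and the assessed group will still be selected by remaining on study. The displayed count makes that selection visible but does not remove it.

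For SAP 9.8, a statement that QTc change categories use patients with a baseline and at least one post-baseline value would be an optional minor clarification.
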